8.2. Classification of an Adverse Event

8.2.1. Severity of Event

The intensity or severity of each AE must be assessed according to the following classifications:

Table 8.2.1A Intensity or Severity Definitions

Mild	Awareness of signs, symptoms, or events that are otherwise easily tolerated that may result in minimal transient impairment of a body function or damage to a body structure, but do not require intervention other than monitoring.
Moderate	Any event that results in moderate transient impairment of a body function or damage to a body structure that causes interference with usual activities, or that warrants possible intervention, such as the administration of medication, to prevent permanent impairment of a body function or damage to a body structure.
Severe	Any event that is incapacitating (an inability to do usual activities) or is life-threatening and results in permanent impairment of a body function or damage to a body structure, or requires intervention, such as major surgery, to prevent permanent impairment of a body function or damage to a body structure.

8.2.2. Relationship to Study Device and/or Procedure

The clinician who examines and evaluates the participant will determine the AE's causality based on temporal relationship and his/her clinical judgment. The degree of certainty about causality will be graded using the categories below. Refer to Sections 8.5 and 8.6 regarding CEC and DMC interactions respectively.

Table 8.2.2A Adverse Event Causality Classifications

Caused By	Relation	Definition of Relation
Device	Causal relationship	The event is associated with the investigational device beyond reasonable doubt
	Probable	The relationship with the use of the investigational device seems relevant and/or the event cannot reasonably be explained by another cause, but additional information may be obtained
	Possible	The relationship with the use of the investigational device is weak but cannot be ruled out completely
	Unlikely	The relationship with the use of the investigational device seems not relevant and/or the event can be reasonably explained by another cause, but additional information may be obtained
	Not related	Relationship to the investigational device can be excluded
Study Procedure	Causal relationship	The event is associated with the study procedure beyond reasonable doubt
	Probable	The relationship with the study procedure seems relevant and/or the event cannot reasonably be explained by another cause, but additional information may be obtained
	Possible	The relationship with the study procedure is weak but cannot be ruled out completely
	Unlikely	The relationship with the study procedure seems not relevant and/or the event can be reasonably explained by another cause, but additional information may be obtained
	Not related	Relationship to the procedure can be excluded

8.2.3. Outcome

The outcome of each AE must be assessed according to the following classifications:

Table 8.2.3A Adverse Event Outcome Classifications

Classification		Definition
Recovered/Resolved		Subject fully recovered with no observable residual effects
Recovered/Resolved with sequelae		Subject recovered with observable residual effects
Recovering/Resolving	Improved	Subject's condition improved, but residual effects remain
	Unchanged	AE is ongoing without changes in the overall condition
	Worsened	Subject's overall condition worsened
Fatal		Subject died as a result of the AE (whether or not the AE is related to the device or procedure)

8.3. Time Period and Frequency for Adverse Event Assessment and Follow-up

Adverse events shall be assessed and documented starting at the point the subject is considered enrolled (after the patient is consented, imaging screening committee approval is received, pre-procedure angiogram is completed and the treating physician confirms the subject meets all eligibility criteria) and at all study follow-up visits. Each investigator shall provide source documentation as requested by the Sponsor to facilitate reporting and adjudication of these events. Adverse events that occur during this study should be treated by established standards of care which will protect the life and safety of the subject. Events will be followed for outcome information until resolution, stabilization or the subject exits the study, whichever occurs first. Each investigator shall provide source documentation as requested by the Sponsor to facilitate reporting and adjudication of these events.

8.4. Reporting Procedures

8.4.1. Adverse Event Documentation and Reporting Requirements

Reportable adverse events will be recorded and reported on the eCRFs throughout the study and provided to the Sponsor. (In the event EDC is unavailable, adverse events can be notified via email to the NAPA IDE study mailbox: [contact]. Note: the adverse event(s) will still need to be recorded on eCRFs once EDC is functional.)

- If an adverse event occurs, all sections of the Adverse Event eCRF must be completed
- In the case of serious device effects and device deficiencies that could have led to serious adverse device effects, the Sponsor will determine whether the risk analysis needs to be updated and whether corrective or preventative action is required.

- Copies of all relevant source documentation (i.e. procedure reports, physician/nursing notes, discharge summary, etc.) should be compiled and provided to the Sponsor for the adjudication process for all AEs recorded in the study.

Timing for reporting the different types of AEs and Device Deficiencies is described in Table 8.4.1A.

Table 8.4.1A Adverse Event Reporting Requirements

Type of Adverse Event	Reporting Requirements

• SAE• SADE• USADE• Death• Any study device malfunctions that could have led to an SADE*	Report to Sponsor immediately upon study site staff awareness of event but no later than 72 hours
UADE	Report to Sponsor immediately upon study site staff awareness of event but no later than 72 hours, followed by a written report within 10 working days after investigator first learns of the effect to Sponsor and IRB

• All other adverse events• All other study device malfunctions*	Report to Sponsor immediately upon study site staff awareness but no later than 14 calendar days

* Non-study device malfunctions should be reported via the manufacturer's complaints handling process.

The Investigator will report all of the above to the reviewing IRB according to the local reporting requirements.

8.4.2. Serious Adverse Event Reporting

All SAEs, whether or not they are related to the device or procedure, must be reported to the Sponsor, via eCRF, **immediately upon study site staff awareness of event but no later than 72 hours** by the study site personnel. (In the event EDC is unavailable, adverse events can be notified via email to the NAPA IDE study mailbox: [contact]. Note: the adverse event(s) will still need to be recorded on eCRFs once EDC is functional.)

The study investigator shall report the SAE to the reviewing IRB in accordance with the local IRB requirements.

8.4.3. Unanticipated Adverse Device Effect Reporting

All UADE/SADE/USADEs must be reported to the Sponsor, via eCRF, **immediately upon study site staff awareness of the event but no later than 72 hours after study site staff awareness of the event**. (In the event EDC is unavailable, adverse events can be notified via email to the NAPA IDE study mailbox: [contact]. Note: the adverse event(s) will still need to be recorded on eCRFs once EDC is functional.) An investigator shall submit to the reviewing IRB and the Sponsor a written report of any unanticipated adverse device effect occurring during an investigation no later than 10 working days after the investigator first learns of the effect.

Sponsor must immediately conduct an evaluation of a UADE and must report the results of the evaluation to FDA, all reviewing IRBs, and participating investigators within 10 working days after the Sponsor first receives notice of the effect (§§ 812.46(b), 812.150(b)(1)).

A Sponsor who determines that a UADE presents an unreasonable risk to subjects shall terminate all investigations or parts of investigations presenting that risk as soon as possible. Termination shall occur not later than 5 working days after the Sponsor makes this determination and not later than 15 working days after the Sponsor first received notice of the effect. 21 CFR 812.46(b)(2).

8.5. Clinical Events Committee

The Clinical Events Committee (CEC) will consist of a minimum of three independent physicians with expertise in neurosurgery, neurology or interventional neuroradiology and who are not otherwise involved with the study. The CEC will review all reportable adverse events to adjudicate the safety endpoint, in addition to AEs of interest specified in the CEC charter.

8.6. Data Monitoring Committee

An Independent DMC will be responsible for assessing all reported AEs and monitoring the accumulated interim data on a periodic basis as the study progresses to ensure subject safety. The DMC will be comprised of representatives from multiple disciplines including but not limited to neurosurgery, neurology, interventional neuroradiology and biostatistics. The DMC will advise the Sponsor regarding the continuing safety of subjects and those yet to be recruited to the study, as well as the continuing validity and scientific merit of the study. The DMC will provide recommendations to the Sponsor regarding stopping or continuing enrollment in the study. The DMC will operate according to an approved charter.

9. Clinical Monitoring

Clinical site monitoring is conducted to ensure that the rights and well-being of human subjects are protected, that study data are accurate, complete, and verifiable, and that study conduct is in compliance with 21 CFR 812 and 50, ISO 14155, the currently approved protocol, with Good Clinical Practices, and with applicable regulatory requirements. Each site will undergo periodic monitoring visits, and subject medical records shall be made available during the visits.

Monitoring visits may include but are not limited to the following:

- Protocol adherence
- Source documentation verification and accuracy of the eCRFs
- Verification that informed consent is being obtained for all subjects participating in the study in accordance with requirements described in the study protocol
- Verification of completeness of the Regulatory Binder
- Verification of accuracy of all study logs such as the Delegation of Responsibility Log, Device Accountability, etc.
- Compliance with applicable regulations
- Identification and action to resolve any issues or problems with the study.

Data are to be submitted promptly via eCRF after collection. Missing or unclear data will be queried to be corrected as necessary throughout the study. Pulsar Vascular, Inc. will request further documentation such as physician notes, outside hospital records, etc. when further documentation is required to understand any adverse events. Monitoring will be conducted in accordance with the monitoring plan.

10. Statistical Methodology

The following sections provide a general description of the statistical plan for the analysis of study data. A separate Statistical Analysis Plan (SAP) document that provides greater detail on data derivations and the analyses to be performed will be developed and approved prior to the first DMC data analysis report. The SAP will reflect the protocol and any amendments that have been implemented at the time the SAP is finalized. Any deviations from the final SAP will be noted in the final clinical summary report.

10.1. Primary and Secondary Endpoints, and Associated Hypotheses

10.1.1. Primary Endpoints and Associated Hypotheses

The primary safety endpoint is the composite of Neurological Death or Major Ipsilateral Stroke (in downstream territory) up to 1 year post-procedure. The primary effectiveness endpoint is the rate of complete aneurysm occlusion (Raymond I) without significant parent artery stenosis (> 50% stenosis) or re-treatment at 1 year post-procedure.

To establish performance goals for safety and effectiveness for the treatment of wide neck bifurcation aneurysms (WNBAs), Fiorella et al. conducted a meta-analysis of literature published from 2000 via PubMed. A complete description of the systematic literature review and analysis can be found in the article. In summary, articles were identified using predetermined search terms and subsequently screened for inclusion/exclusion resulting in 43 unique references and 53 unique articles for effectiveness and safety, respectively. Sub-group analyses by aneurysm location (anterior vs. posterior) and treatment modality (surgical clipping (SC) and endovascular treatment (EVT) was also performed. A composite safety endpoint of major adverse events was applied with effectiveness outcomes reported as complete occlusion (Raymond I) and adequate occlusion (Raymond I and II) with at least one follow-up image at 12 months (range 4-25 months) post procedure. Notably, a 12% adjustment for non-core laboratory adjudicated images was made. The authors reported adequate occlusion rates for all therapies as 59.4% and 43.8% and 69.7% for EVT and SC, respectively. The rates of occurrence for pre-specified safety endpoints were 18.7% combined, and 21.1% and 24.3 % for EVT, and SC, respectively.

Considering the similarities in the NAPA IDE target subject population and primary effectiveness endpoint (complete occlusion at 1 year post-procedure) to that which was evaluated in Fiorella et. al., the incidence of 46.3 % reported in the meta-analysis was used to generate a proposed NAPA IDE performance goal for effectiveness of 46.3%. Based on the experience with the ANSWER study which evaluated the PulseRider device, the rate of adequate occlusion with the PulseRider device is expected to be at least 58.8%.

The composite safety endpoint applied by Fiorella et al. is reasonably dissimilar to the NAPA IDE primary safety endpoint of major ipsilateral stroke or death due to neurological causes at 1 year post-procedure. As a result, the NAPA IDE performance goals for safety was determined from a systematic review of literature published in OVID and PubMed between January 1, 2012 and April 25, 2017. After de-duplication, a full text search in QUOSA was performed limiting results to WNBA located at NAPA IDE aneurysm locations. The following inclusion/ criteria were applied, yielding 7 unique articles for safety with Forest Plot shown in Figure 10.1.1A. [Brassel 2015, Fields 2011, Labeyrie 2017, Pierot 2015, Peirot 2015 Sivan-Hoffman 2015, Zhao 2012].

Included articles:

- Article reporting clinical performance and safety results on equivalent comparator(s) [WEB, pCONUS, BARREL, X/Y stenting]
- Wide neck or complex bifurcation aneurysms found at MCA, ACOM, Basilar tip, carotid terminus with at least 80% or more unruptured aneurysms and where ≥ 5 patients were included in a series
- Clinical follow-up between 10 and 14 months;

[figure not shown]
Excluded articles:

- Technical or reviews (systematic and none) with non-extractable data by treatment modality

- No clinical performance and safety results on target device(s) and/or equivalent comparator(s)
- Use of the target device(s) and/or equivalent comparator(s) was not the main focus of the study
- Studies where the subject device was used in patients, but no safety or performance outcomes were reported
- Abstract, report, or article could not be retrieved
- Duplicate or non-English articles language

Of the included articles, all reported safety events were evaluated and neurological deficits that resulted in a sudden change in NIHSS of 4 or more (when reported) or as determined by a Codman neurosurgeon to cause a change in NIHSS of 4 or more were deemed to meet the primary safety endpoint. Based on this meta-analysis, a rate of 9.9% rounded to 10% (95% CI: 5.9% - 16.1%) for death due to neurological causes or major ipsilateral stroke was identified. A 5% margin of indifference for the primary safety endpoint is proposed, resulting in a Performance Goal (PG) of 15% for this endpoint.

Figure 10.1.1A Forest Plot: Seven References with Usable Data to Estimate the Anticipated Primary Safety Endpoint at 12 Months

Primary Safety Endpoint Hypotheses:

Null Hypothesis H_0 : $p_{\text{Major Stroke/Death}} \geq 15\%$

Alternative hypothesis H_A : $p_{\text{Major Stroke/Death}} < 15\%$

Where $p_{\text{Major Stroke/Death}}$ is the rate of Composite of Neurological Death or Major Ipsilateral Stroke (in downstream territory) up to 1 year post-procedure.

Decision Criterion: The decision will be made to reject the null hypotheses and conclude the alternative hypothesis if the upper bound of a two-sided 95% normal approximation based confidence interval is < 15%.

Primary Effectiveness Endpoint Hypotheses:

Null hypothesis H_0 : $p_{\text{CompleteOcclusion}} \leq 46.34\%$

Alternative hypothesis H_A : $p_{\text{CompleteOcclusion}} > 46.3\%$

Where $p_{\text{CompleteOcclusion}}$ is the rate of complete aneurysm occlusion without significant parent artery stenosis ($> 50\%$ stenosis) or prior retreatment at 1 year post-procedure.

Decision Criterion: The decision will be made to reject the null hypotheses and conclude the alternative hypothesis if the lower bound of a two-sided 95% normal approximation based confidence interval is $> 46.3\%$.

Study Success:

The study will be deemed to be a success if the primary safety and effectiveness endpoint null hypotheses are both rejected.

10.1.2. Secondary Endpoints

- Technical Success is defined as successful implantation of device— physician able to access target aneurysm, deploy PulseRider device at the neck of aneurysm and device was detached successfully. This endpoint will be reported by the investigator. The following hypothesis test of this endpoint will be performed if the primary safety and effectiveness endpoint null hypotheses are both rejected:
 - Null hypothesis H_0 : $p_{\text{TechnicalSuccess}} \leq \text{PG of } 79\%$
 - Alternative hypothesis H_A : $p_{\text{TechnicalSuccess}} > \text{PG of } 79\%$
 - Where $p_{\text{TechnicalSuccess}}$ is the rate of technical success
 - Decision Criterion: The decision will be made to reject the null hypotheses and conclude the alternative hypothesis if the lower bound of a two-sided 95% normal approximation based confidence interval is $> \text{PG of } 79\%$. With 160 subjects, a rate for technical success of at least 85% is required to demonstrate success on this endpoint.
- Ability to retain embolic coils within aneurysm immediately post-procedure (as evaluated by the core lab)
- Complete aneurysm occlusion at 3 years and 5 years. Complete aneurysm occlusion is defined as Raymond I. Aneurysm occlusion grading will be evaluated by the independent core laboratory.
- Adequate aneurysm occlusion (defined as Raymond I and II combined) at 1 year, 3 years and at 5 years. Aneurysm occlusion grading will be evaluated by the independent core laboratory.
- The percentage of target aneurysms that are retreated through 1 year, 3 years and 5 years. Retreatment will be reported by the investigator.

- The percentage of subjects with significant stenosis defined as $> 50\%$ at implant site at 1 year, 3 years and 5 years. This endpoint will be evaluated by the independent core laboratory
- The percentage of subjects with mRS 0 – 2 at 1 year, 3 years and 5 years

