3.2.2. Primary Endpoint - Effectiveness

Complete Occlusion:

Rate of complete aneurysm occlusion (Raymond I) without significant parent artery stenosis ($> 50\%$ stenosis) or prior retreatment at 1 year post-procedure.

The aneurysm occlusion and parent artery stenosis assessments in this endpoint will be evaluated by the independent core laboratory. Retreatment will be reported by the site.

Figure 3.2.2A Raymond Scale [Roy 2001]

- **Class I: Complete** = Complete obliteration
- **Class II: Residual Neck** = Persistence of any portion of the original defect of the arterial wall but without opacification of the aneurysmal sac
- **Class III: Residual Aneurysm** = any opacification of the aneurysm sac

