7.11. Retreatment

At the discretion of the investigator, a subject who has received a PulseRider device may be retreated (e.g. with coils, stent, etc.) at any time. All subjects who are retreated will remain in the study and will continue to receive all follow-up assessments based on the date of the index procedure per the Schedule of Assessments in Section 7.15. When a subject returns for a retreatment, this is considered an unscheduled visit and the evaluations noted for unscheduled visits must be completed. Data from the retreatment procedure will be captured in the appropriate eCRF, and data from the remaining unscheduled assessments will also be captured in the eCRFs. No pre-planned staged procedures on target aneurysms will be allowed in the study.

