Success on this endpoint is defined as complete aneurysm occlusion (Raymond I) without retreatment or significant parent artery stenosis (> 50% stenosis) at 1 year post-procedure. If the 1 year imaging is not available and if the subject did not experience a retreatment then the subject will be imputed using an imputation method that will make use of the subject's own past occlusion and stenosis evaluations if available and the similarities between the subject's demographic, procedural, and aneurysm characteristics with those of the subjects with a non-missing endpoint.

The multiple imputation method results in a large collection of imputed datasets. The proportion of complete aneurysm occlusion and its variance is computed for each dataset. Within and between imputation variances are then combined according to Rubin's method in order to produce a single variance estimate for the proportion of complete aneurysm occlusion.

The endpoint will be considered successful if the lower bound of the 2-sided 95% normal approximation based confidence interval for the rate is greater than a performance goal of 46.3%.

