10.3.5. Secondary Endpoint Analyses

The analysis of technical success which is reported by the investigator will be conducted on the mITT analysis set. The endpoint will be considered successful if the lower bound of the 2-sided 95% normal approximation based confidence interval for the rate is greater than a performance goal of 79%.

The analyses of the remaining secondary effectiveness endpoints listed below will be conducted on the PP analysis set using the observed data.

- The ability to retain embolic coils within aneurysm immediately post-procedure as reported by the independent core laboratory
- Complete aneurysm occlusion at 3 years and 5 years as reported by the independent core laboratory
- Adequate aneurysm occlusion at 1 year, at 3 years and 5 years as reported by the independent core laboratory
- The percentage of target aneurysms that are retreated through the 1 year, 3 year and 5 year as reported by the investigator
- The percentage of subjects with significant stenosis defined as > 50% at implant site at 1 year, 3 years and 5 years as reported by the independent core laboratory
- The percentage of subjects with mRS 0-2 at 1 year, 3 years and 5 years

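### The later occlusion endpoints carry no retreatment condition, so a retreated aneurysm graded Raymond I (or I/II) counts as a success, although the primary endpoint counts it as a failure

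*Combined protocol and SAP*

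**What the plan says.** The primary effectiveness endpoint names retreatment as a failure. Section 3.2.2 requires Raymond I without significant stenosis "or prior retreatment at 1 year post-procedure". Section 10.1.1 repeats the condition in the hypotheses, and section 10.3.4 repeats it in the analysis rule: "Success on this endpoint is defined as complete aneurysm occlusion (Raymond I) without retreatment or significant parent artery stenosis". That sentence is limited to the primary endpoint.

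The secondary occlusion endpoints carry no such condition wherever they are stated (Protocol Summary and sections 3.2.3, 10.1.2 and 10.3.5). Section 10.1.2 has "Complete aneurysm occlusion at 3 years and 5 years. Complete aneurysm occlusion is defined as Raymond I" and "Adequate aneurysm occlusion (defined as Raymond I and II combined) at 1 year, 3 years and at 5 years". Section 10.3.5 takes these rates from the core laboratory, for example "Adequate aneurysm occlusion at 1 year, at 3 years and 5 years as reported by the independent core laboratory", in the per-protocol set with observed data.

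Under section 7.11 a subject "may be retreated (e.g. with coils, stent, etc.) at any time", and "All subjects who are retreated will remain in the study and will continue to receive all follow-up assessments". Section 10.1.6 restricts the per-protocol set by eligibility deviations, antiplatelet deviations and implant success, but not by retreatment. Retreatment is reported by the investigator as a separate secondary percentage through 1, 3 and 5 years.

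**The concern.** The same event is handled in two ways. At the 1-year visit, on the same image, a retreated subject fails the primary endpoint but can count as adequately occluded. At 3 and 5 years, a retreated aneurysm that is graded Raymond I counts as completely occluded. A repair made after the index treatment is then credited to that treatment.

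These are the plan's only occlusion rates beyond 1 year, and section 2.1 says that the data will support a premarket application. The 1-year primary rate and the 3- and 5-year rates are all called complete occlusion, but only the first excludes retreated aneurysms. A reader who follows the rate over time could take closure by a second procedure for durability of the first.

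**Working it through.** **1. Does any other rule remove retreated aneurysms?**

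| Step | Source | Result |
|---|---|---|
| Is retreatment a failure in the definition? | 3.2.3, 10.1.2, 10.3.5 | No condition stated |
| Does the primary rule carry over? | 10.3.4 | No; it is limited to that endpoint |
| Do retreated subjects leave follow-up? | 7.11 | No; they keep all scheduled assessments |
| Do they leave the analysis set? | 10.1.6 | No; retreatment is not an exclusion |
| Does the grading account for retreatment? | 6.2.3, 3.2.3 | Not stated; the core laboratory grades the image blinded to previous medical history, and retreatment comes from the investigator |

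Nothing in the chain stops a retreated aneurysm with a qualifying grade from being counted as a success.

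**2. The plan's own figure.** The secondary occlusion endpoints have no target or power. The only occlusion endpoint with a design figure is the primary: 85% power, 58.8% expected against a performance goal of 46.3%, 160 enrolled, 10% attrition (section 10.2).

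- Evaluable n = 160 × 0.9 = 144.
- Standard error under the alternative = √(0.588 × 0.412 / 144) = 0.0410.
- Power = Φ(0.125 / 0.0410 − 1.96) = Φ(1.09) = 86.2%.
- With the null variance it is 85.6%, and by exact binomial calculation 85.2%.

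The stated 85% is reproduced. It concerns the primary endpoint, which already excludes retreated aneurysms, so this point does not change it.

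**3. Size of the overstatement.** Let r be the share of imaged subjects retreated before the visit, and s the share of those graded a success at the visit. Counting retreated subjects as failures lowers the rate by r × s. Because s cannot exceed 1, the fall cannot exceed r.

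The documents give neither r nor s for this trial. Section 1.3.2 reports two secondary procedures among 34 subjects in the earlier study: 2/34 = 5.9% (exact 95% interval 0.7% to 19.7%). It does not say that these were retreatments of the target aneurysm, so 5.9% is an assumed value. The other values of r, and all values of s, are assumptions too.

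| r (assumed) | s = 50% | s = 100% |
|---|---|---|
| 3% | 1.5 points | 3.0 points |
| 5.9% | 2.9 points | 5.9 points |
| 10% | 5.0 points | 10.0 points |
| 15% | 7.5 points | 15.0 points |

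At r = 5.9% and n = 144 this is 144 × 0.0588 × 0.5 = 4.2 to 144 × 0.0588 × 1 = 8.5 subjects. The number imaged at 3 and 5 years is not given and may be below 144. At 1 year fewer retreatments will have accrued than at 5 years, so the upper rows fit the later visits better.

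**The case against.** **The gap is an omission.** No sentence says that a retreated aneurysm is a success, and it counts only if the core laboratory grades it so. Section 10 also calls itself a general description and leaves derivation detail to a separate SAP, which is not in the text reviewed. This stands as a limit on certainty. But section 10 also says that the SAP will follow the protocol, and the protocol's definition is the grade alone.

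**Nothing is tested.** Technical success is the only secondary endpoint with a performance goal and a test. A reader might infer that study success is at risk. It is not, because both primary endpoints are unaffected.

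**Retreatment is already reported.** It is a separate endpoint at the same time points, so a reader can roughly bound the effect by subtraction. That holds, apart from differences between the retreatment and imaging denominators. Without a cross-tabulation, however, the reader cannot see how many counted successes had been retreated.

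**The rates need not rise with failure.** A reader might infer that the more aneurysms fail and are retreated, the higher the rates go. That does not follow. An aneurysm that was occluded, recurs and is closed again only returns to its former grade: the loss is hidden, but the rate does not rise. Retreating a Raymond II aneurysm does not raise the adequate rate either. A rise needs retreatment to close an aneurysm that did not already meet the grade.

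**Status regardless of retreatment is a legitimate description.** It is, when it is labelled as such. Here it shares a name with a primary endpoint that excludes retreatment, and it carries no label.

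**Conclusion.** The point holds in a limited form. By their stated definitions, complete occlusion at 3 and 5 years and adequate occlusion at 1, 3 and 5 years count a retreated aneurysm with a qualifying grade as a success, against the rule for the primary endpoint. The change should be made, but the trial's conclusion does not depend on it.

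The overstatement is r × s, capped at the share of imaged subjects who were retreated. On assumed inputs it is about 3 to 6 points at 5.9% retreated, and 1.5 to 15 points across 3% to 15%. The definitional gap does not depend on those assumptions; only its size does.

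A reader might also infer that adding a retreatment condition would make the later rates directly comparable with the 1-year primary. The documents do not support that. The primary also requires absence of stenosis above 50%, uses multiple imputation, and rests on catheter angiography alone. The later rates have no stenosis condition, use observed data, and at 3 and 5 years accept MR angiography.

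**What to change.** In sections 3.2.3, 10.1.2 and 10.3.5, and in the Protocol Summary to match, define complete occlusion at 3 and 5 years and adequate occlusion at 1, 3 and 5 years as the stated Raymond grade without retreatment of the target aneurysm before that visit's image. Count retreated subjects as failures. Report the grade regardless of retreatment beside it as a labelled supporting line.

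The wording should also say whether a retreated subject with no image at that visit enters the denominator as a failure. The figures above keep to imaged subjects.

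The cost is a wording change in the protocol and SAP. Retreatment is already captured on the case report form, so no new data, visits or subjects are needed. The headline rates will be somewhat lower. The differences from the primary in stenosis condition, missing-data handling and imaging modality remain and should be noted wherever the rates are shown together. Setting the rule before the 3- and 5-year data are seen avoids a choice made after the fact.
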